10.1.3. Serious Adverse Event

An SAE is defined as any untoward medical occurrence at any dose that:

- Results in death
- Is immediately life-threatening (places the participant at immediate risk of death from the event as it occurred)

- Requires inpatient hospitalization or prolongation of existing hospitalization
- Results in persistent or significant disability or incapacity or substantial disruption of the ability to conduct normal life functions
- Results in a congenital abnormality or birth defect
- Is an important medical event that may not result in death, be life-threatening, or require hospitalization, but may be considered an SAE when, based upon appropriate medical judgment, it may require medical or surgical intervention to prevent any of the outcomes listed above

PTAEs that fulfill any of the criteria above are also to be considered SAEs and should be reported and followed up in the same manner.

- The terms "severe" and "serious" are not synonymous. Severity refers to the intensity of an AE (eg, rated as mild, moderate, or severe); the event itself may be of relatively minor medical significance (such as severe headache without any further findings).
- An AE of severe intensity need not necessarily be considered serious. For example, nausea that persists for several hours may be considered severe nausea but not an SAE. On the other hand, a stroke that results in only a limited degree of disability may be considered a mild stroke but would be an SAE.
- Severity and seriousness need to be independently assessed for each AE recorded on the eCRF.
- SAEs are required to be reported by the Investigator to the Sponsor within 24 hours after learning of the event.

10.1.4. Adverse Events of Special Interest

Symptomatic overdose, outcomes of a pregnancy, and LVEF \leq 30% are considered AESIs.

AESIs are required to be reported by the Investigator to the Sponsor within 24 hours, irrespective of regulatory seriousness criteria.

10.2. Collection and Reporting of Adverse Events

10.2.1. Pretreatment Adverse Events and Adverse Events Collection Periods

Collection of PTAEs will commence from the time the participant signs the informed consent to participate in the study and continue until the participant receives the first dose of study drug. For participants who discontinue prior to study drug administration, PTAEs are collected until the participant discontinues study participation.

Collection of treatment-emergent adverse events (TEAEs) (as defined in [Section 10.1.2](#)) will commence at the time the participant receives the first dose of study drug. Routine collection of TEAEs will continue until the end of the study. Assessments of the relationship of AEs to study drug will be captured for TEAEs and not PTAEs.

10.2.2. Pretreatment Adverse Events and Adverse Events Reporting Periods

At each study visit, the Investigator will assess whether any subjective AEs have occurred. A neutral question, such as “How have you been feeling since your last visit?” may be asked. Participants may report AEs occurring at any other time during the study.

All participants experiencing PTAEs or TEAEs, whether considered associated with the use of the study drug or not, must be monitored until the symptoms subside and any clinically relevant changes in laboratory values have returned to screening levels or until there is a satisfactory explanation for the changes observed. All PTAEs and TEAEs will be documented in the PTAE/AE page of the eCRF, whether or not the Investigator concluded that the event was related to the study drug. The information to be documented for each event is described in the following sections.

10.2.2.1. Event description

When collecting PTAEs and TEAEs, the recording of diagnoses is preferred (when possible) to recording a list of signs and symptoms (eg, anemia, not low hemoglobin). However, if a diagnosis is known and there are other signs or symptoms that are not generally part of the diagnosis, the diagnosis and each sign or symptom will be recorded separately.

Death is an outcome and not the name of the event. In this situation, the event that led to the death is the name of the event.

10.2.2.2. Start Date/Time and Stop Date/Time

The date (and time during the period of residency) that the PTAE or TEAE started and the date (and time during the period of residency) that the event ended will be recorded. For events that continue for long periods of time, recording the end date as the day the event stabilized will be acceptable.

10.2.2.3. Relationship to Study Drug (Suspected Adverse Reactions)

The Investigator will assess causality by answering either “related” or “not related” to the question “Is there a reasonable possibility that the event may have been caused by the IMP/study medication?”

The following factors can be used in consideration of causality assessment:

- Dechallenge: Did the event abate after study medication was reduced or interrupted?
- Rechallenge: Did the event reappear after study medication was reintroduced?
- Temporal relationship and time to onset plausibility
- Confounding risk factors
- Amount and duration of study drug exposure
- Concomitant medications

10.2.2.4. Severity/Intensity

The intensity or severity of the PTAE or TEAE will be recorded using the following guidance:

- Mild (awareness of sign or symptom, but easily tolerated)
- Moderate (discomfort sufficient to cause interference with normal activities)
- Severe (incapacitating, with inability to perform normal activities)
- Life-threatening (urgent intervention indicated)
- Fatal (event led to death)

10.2.2.5. Seriousness

A PTAE or TEAE that meets any of the criteria for an SAE outlined in [Section 10.1.3](#) will be recorded as an SAE, along with the criteria that were met.

It is important to distinguish between seriousness (PTAE or AE compared with SAE) and severity/intensity (mild, moderate, severe, life-threatening, or fatal) of AEs as outlined in [Section 10.2.2.4](#).

10.2.2.6. Outcome

The outcome of a PTAE or TEAE will be recorded according to the options provided on the eCRF.

10.2.3. Reporting of Serious Adverse Events

All SAEs occurring during the treatment-emergent period (defined as the period from the first dose of study drug to the last dose of study drug + 56 days), regardless of causality, will be reported by the Investigator or designee to MyoKardia/designee within 24 hours of knowledge of the event or sequelae. Deaths and SAEs occurring after the treatment-emergent period and considered related to study drug or study procedure must also be reported. SAE reporting instructions are provided in the Study Reference Manual.

Medical records may be requested to support documentation of an SAE. The Investigator is responsible for summarizing the pertinent aspects of the event (including discharge summaries, diagnostic procedures, laboratory data, interventions) and updating the SAE eCRF with this information.

MyoKardia retains the right to request additional information for any participant with any ongoing AEs/SAEs at the end of the study, if judged necessary.

Spontaneously reported SAEs after completion of the study should be promptly reported by the Investigator to the Sponsor.

Prompt notification by the Investigator to the Sponsor of SAEs is essential so that legal obligations and ethical responsibilities for the safety of participants and the safety of a study intervention under clinical investigation are met.

10.2.4. Follow-Up of Adverse Events and Serious Adverse Events

After the initial AE/SAE report, the Investigator is required to proactively follow each participant at subsequent visits/contacts. All AEs, SAEs, and AESIs, will be followed until

resolution, stabilization, the event is otherwise explained, or the participant is considered lost to follow-up at the end of the study.

10.3. Suspected Unexpected Serious Adverse Event Reactions

Suspected unexpected serious adverse reactions (SUSARs) are SAEs that qualify for mandatory expedited reporting to regulatory authorities where the SAE is suspected to be caused by the study treatment and is considered unexpected (ie, not defined as expected in the current IB, clinical protocol, or approved labeling for marketed products). In this case, MyoKardia or its designee will report the SUSAR to the relevant regulatory authority(ies). A report describing the SUSAR will be sent to all Investigators. Each Investigator must then notify his/her ethics committee (EC) of the SUSAR, as required by local regulatory authorities and in accordance with their EC policy.

11. STATISTICAL METHODS

11.1. Determination of Sample Size

No statistical hypothesis testing will be performed in this long-term extension study. Up to 20 individuals with symptomatic oHCM who completed Study MYK-461-004 will be enrolled.

11.2. Study Endpoints

11.2.1. Safety Endpoints

- Frequency and severity of treatment-emergent AEs and SAEs
- Frequency of cardiovascular (CV) death
- Frequency of sudden death
- Frequency of CV hospitalization
- Frequency of heart failure due to systolic dysfunction, defined as a symptomatic LVEF < 50%
- Frequency of myocardial infarction
- Frequency of ventricular arrhythmias (ventricular tachycardia, ventricular fibrillation, ventricular flutter, torsade de pointe)
- Frequency of syncope
- Frequency of seizures
- Frequency of stroke
- Frequency of LVEF < 50% as measured by echocardiography
- QT and QTcF intervals over time

11.2.2. Efficacy and Pharmacodynamic Endpoints

- Post-exercise, post-Valsalva, and resting LVOT gradient over time
- NYHA functional class over time
- KCCQ scores over time
- NT-proBNP over time
- Frequency of septal reduction therapy

11.2.3. Pharmacokinetic Endpoints

- Mavacamten plasma concentration over time
- Population PK

11.3. Statistical Analysis

The analyses presented here represent an outline of the intended methodology.

11.3.1. Analysis Populations

Three analysis populations are defined in this study:

- Safety Analysis Population: all participants who receive at least 1 dose of study drug
- PK Analysis Population: all participants who receive at least 1 dose of study drug and have at least 1 evaluable mavacamten plasma drug concentration
- PK/PD Analysis Population: all participants who receive at least 1 dose of study drug, have at least 1 evaluable mavacamten plasma drug concentration, and have post-baseline PD data; at least one 1 post-baseline PD data point must coincide temporally with an evaluable mavacamten plasma drug concentration

11.3.2. General Considerations

Data will be summarized in tabular format and concentration response plots may be constructed for selected variables. The sparse PK data will be combined with that of other studies to construct a population PK model across all studies.

Descriptive summary statistics for continuous variables will include the number of participants, mean, standard deviation (SD) or standard error, median, minimum, and maximum. Nominal categorical variables will be summarized using counts and percentages. Ordinal variables may be tabulated but no formal statistical test will be conducted.

11.3.3. Participant Disposition

The number and percentage of participants who complete and discontinue, as well as reasons for early discontinuation, will be presented.

11.3.4. Demographics and Baseline Characteristics

Demographic and baseline characteristics will be summarized descriptively.

11.3.5. Extent of Study Treatment Exposure and Compliance

The extent of study treatment exposure and compliance will be assessed and summarized by actual treatment received within the safety population.

The duration of study drug exposure is defined as last dose date – first dose date + 1 day, regardless of intermittent discontinuations.

A given administration will be considered noncompliant if the participant did not take the planned dose of treatment as required by the protocol. No imputation will be performed for participants with missing or incomplete data.

Treatment compliance will be summarized descriptively (number [n], mean, SD, median, minimum, and maximum). Participants with compliance < 80% will be fully described and summarized. In addition, number and percentage of participants with at least 1 dosing administration will be given.

11.3.6. Efficacy and Pharmacodynamic Analyses

All efficacy and PD analyses will be performed on the safety population.

11.3.7. Pharmacokinetic Analyses

Plasma concentrations of mavacamten will be determined and summarized using descriptive statistics. In addition, a PK analysis, as well as PK/PD analysis, will be performed using nonlinear mixed effect modeling. Both analyses will be reported in separate reports. Data from previously conducted studies might be added for model development for PK and PK/PD.

11.3.8. Safety Analyses

All safety analyses will be performed on the Safety Analysis Population using the following common rules:

- The baseline value is defined generally as the last available value before the first administration of study drug
- For quantitative safety parameters based on central laboratory measurements, descriptive statistics will be used to summarize results and change from baseline values by visit and treatment group; said changes may be presented in shift tables or scattergrams
- The analysis of the safety variables will be descriptive, and no hypothesis testing is planned

The safety analysis will focus on the treatment-emergent period, which is defined as the time from the first administration of study drug to the last administration of study drug + 56 days.

11.3.8.1. Adverse Events

AEs will be mapped to system organ classes (SOCs) and preferred terms (PTs) using the Medical Dictionary for Regulatory Activities (MedDRA). AEs will be monitored during the study and the data analyzed with respect to overall incidence as well as severity and potential relationship of AEs to study medication. AEs with onset during the treatment-emergent period or with an onset

before the first dose of study medication that increases in severity or becomes serious during the treatment-emergent period, will be considered treatment-emergent.

Adverse event incidence tables will present the number (n) and percentage (%) of participants experiencing at least 1 TEAE by SOC and PT. Multiple occurrences of the same event in the same participant will be counted only once in the tables. The denominator for computation of percentages is the safety population within each treatment group.

AE incidence tables will be provided by treatment group for all types of TEAEs: all TEAEs, all treatment-emergent SAEs, and all TEAEs leading to permanent treatment discontinuation.

Potential Drug-induced Liver Injury

The incidence of liver-related AEs will be summarized by treatment group. The selection of PTs will be based on standardized MedDRA query hepatic disorder.

Deaths

- Deaths will be summarized and listed.

Pregnancy

- Participants who became pregnant during the study will be listed.

Overdose

- Onstudy overdoses will be listed.

11.3.8.2. 12-Lead Electrocardiogram

Twelve-lead ECGs will be obtained in the resting supine position. The RR, PR, QRS, and QT intervals will be measured and read by a central laboratory. Heart rate will be calculated as $60/(RR \times 1000)$ (with RR expressed in milliseconds) and rounded to the nearest integer.

Correction for Heart Rate

Corrected QT interval (QTc) will be calculated using the manually over-read QT values. Each individual ECG QT value will be corrected for HR. The measured QT data will be corrected for HR using QTcF, as per the following formulae/method (with QT, RR, and QTc expressed in milliseconds):

Fridericia's Correction:

$$QTcF = \frac{QT}{(RR / 1000)^{(1/3)}}$$

ECG Numeric Variables

HR, PR, QRS, and QTcF will be summarized using descriptive statistics. The change from baseline of these ECG parameters at each time point will be listed for each participant. For each time point of measurement, the changes from baseline will be summarized using descriptive statistics.

Categorical Analysis

The incidence count and percentage of participants with any postdose QTcF values of > 450 milliseconds, > 480 milliseconds, and > 500 milliseconds will be tabulated for all participants. Participants with QTc values > 500 milliseconds will be listed with corresponding baseline values, Δ QTcF, and baseline and treatment HR. The incidence count and percentage of participants with Δ QTcF increase from baseline of > 30 milliseconds and > 60 milliseconds will be tabulated.

Morphology Findings

New ECG morphologies for each participant not present on any ECG at baseline for that participant will be summarized for all observation time points combined.

The number and percentage of participants having T-wave morphology changes and/or the occurrence of abnormal U-waves that represent the appearance or worsening of the morphological abnormality from baseline will be reported.

Concentration-QTc Analyses

A concentration-QTc regression analysis, based on data collected from the ECG recordings after drug administration and concentration values for each participant at each matching time point, will be performed. The concentration-ECG relationship will be first evaluated by some descriptive plots to investigate any potential delayed or sustained effects and explore the shape of the relationship. Then, linear or nonlinear models will be implemented to estimate the slope and 95% confidence intervals of the relationship. Predictions at selected concentration values will be computed within the model.

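### The ECG heart-rate formula in Section 11.3.8.2 multiplies RR by 1000 where it should divide, so as printed every heart rate rounds to 0 (minor, one-line correction)

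*Combined protocol and SAP*

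**What the plan says.** Section 11.3.8.2 (12-Lead Electrocardiogram) gives the formula, the unit and the rounding in one sentence: "Heart rate will be calculated as $60/(RR \times 1000)$ (with RR expressed in milliseconds) and rounded to the nearest integer". The RR values come from central reading: "The RR, PR, QRS, and QT intervals will be measured and read by a central laboratory".

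A few lines later, under Correction for Heart Rate, the Fridericia formula divides QT by the cube root of RR/1000, "with QT, RR, and QTc expressed in milliseconds".

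The derived heart rate is then used in three outputs:

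- Under ECG Numeric Variables, "HR, PR, QRS, and QTcF will be summarized using descriptive statistics".
- Under the same heading, "The change from baseline of these ECG parameters at each time point will be listed for each participant", and these changes are also summarized at each time point.
- Under Categorical Analysis, "Participants with QTc values > 500 milliseconds will be listed with corresponding baseline values", and the same sentence calls for heart rate at baseline and on treatment.

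No other section defines ECG heart rate.

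**The concern.** Two formulas in one section take the same variable in the same unit and convert it in opposite directions. The QTcF formula divides RR by 1000 to reach seconds, while the heart-rate formula multiplies by 1000. Only division gives beats per minute.

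The three outputs that use heart rate are at stake. The listing of QTc values above 500 ms matters most, because there heart rate is the context for judging a rate-corrected interval. Heart rate is also recorded as a vital sign, but Table 2 footnote d has it taken sitting, whereas for the ECG "Twelve-lead ECGs will be obtained in the resting supine position". The vital-sign value is a useful cross-check, but it is not the heart rate of the same tracing.

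**Working it through.** **Inputs.** The heart-rate formula, its unit and its rounding rule, and the QTcF formula and its unit, are from Section 11.3.8.2. The ECG visits are from Table 2, and the maximum enrolment of 20 is from Section 11.1. The documents give no RR values, so RR from 300 to 2000 ms is an assumed range. The plan states no numerical heart rate to reproduce, so the check is a direct evaluation of the rule.

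**Step 1: the rule as printed against the correct conversion.**

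| RR (ms) | Printed: 60/(RR × 1000) | Rounded | Correct: 60/(RR/1000) |
|---|---|---|---|
| 300 | 0.0002 | 0 | 200 |
| 600 | 0.0001 | 0 | 100 |
| 800 | 0.000075 | 0 | 75 |
| 1000 | 0.00006 | 0 | 60 |
| 1200 | 0.00005 | 0 | 50 |
| 2000 | 0.00003 | 0 | 30 |

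The ratio of the two is 1000 × 1000 = 1,000,000 at every RR. The printed rule reaches 0.5 only at RR = 60/(0.5 × 1000) = 0.12 ms, so no real ECG escapes the zero.

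**Step 2: other readings.** Taking RR in seconds, against the stated unit, does not rescue the rule. At RR = 0.8 s it gives 60/(0.8 × 1000) = 0.075, and over the assumed range it gives 0.03 to 0.2, which again rounds to 0. Moving the bracket does rescue it: (60/800) × 1000 = 75.

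**Step 3: change from baseline.** If RR goes from 800 to 1000 ms, the true change is 60 − 75 = −15 bpm. The printed rule reports 0 − 0 = 0.

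**Step 4: what is not affected.** QTcF uses RR, not heart rate. With an assumed QT of 470 ms and RR of 800 ms, QTcF = 470/0.8^(1/3) = 506.3 ms. The participant is correctly listed as above 500 ms, but with a heart rate of 0 instead of 75.

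**Step 5: extent.** Table 2 schedules ECGs at Screening, Day 1 and Weeks 4, 8, 12, 24, 36, 48, 60, 72, 84 and 96, which is 12 visits. With 20 participants attending every visit, the line governs at most 12 × 20 = 240 values through Week 96. Section 11.3.8 generally takes one pre-dose value as baseline. On that basis, one baseline and 10 post-dose values per participant feed the summaries: 11 × 20 = 220. ECGs after Week 96 are not counted, because the Table 3 grid is not legible in the available text.

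**The case against.** The strongest reply is that this is editorial and may not be in the plan at all. The formula was read from a PDF, and one misplaced bracket or one misread operator would turn a correct formula into this one. That possibility stands. Against it, the slash and brackets of the QTcF formula nearby came through intact.

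Second, Section 11.3 describes its content as an outline, and the Amendment 2 change table says the analyses may be documented in an abbreviated document instead of a full SAP. Programming may therefore never follow this sentence. That is fair as to likelihood. But the sentence specifies formula, unit and rounding, and nothing in the reviewed text supplies a correct version.

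Third, no endpoint or decision depends on ECG heart rate. The ECG safety endpoint is QT and QTcF over time. The temporary-discontinuation criteria in Sections 4 and 7.5 use plasma concentration, LVEF, and QTcF with a threshold set by QRS width. No hypothesis is tested. A column of zeros would be seen rather than bias a conclusion. All of this stands, and it is why the point is minor.

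The counts of 240 and 220 are upper limits. They assume full enrolment, full attendance and literal programming.

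**Conclusion.** The rule is wrong as printed. It returns 0 for every possible RR, a factor of 1,000,000 below the correct value, and it conflicts with the conversion used for QTcF in the same section. The arithmetic is certain. The one open assumption is that the PDF carries the same brackets and operator as the text read from it.

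The damage is confined to the ECG heart-rate summaries, the heart-rate changes from baseline and the heart rates in the listing of QTc values above 500 ms. QTcF, its categories, the concentration-QTc analysis and the QTcF discontinuation criteria are untouched. The severity is minor.

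**What to change.** Check the formula in the source PDF. If it reads (60/RR) × 1000, no change is needed. If it stands as printed, replace it with HR (bpm) = 60/(RR/1000) = 60000/RR, with RR in milliseconds, rounded to the nearest integer, and use the same rule in any separate analysis document.

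Section 13.4 already allows obvious errors to be corrected by Administrative Letter. The cost is one line of text, with no change to visits, ECGs, samples or any other analysis. Any heart rates already derived by the printed rule can be recomputed from the stored RR values.
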